4.5 Descriptive Analyses

As in the master protocol, we will use similar descriptive statistics to summarize the observed rates of AESI in the pediatric population. Table 3 lists all the AESI for which we will be conducting descriptive monitoring only. These statistics will be stratified by age group³, sex, region, urban/rural status, and data source. Descriptive statistics will be updated continuously, synchronized with the sequential testing, on a monthly basis, as allowed by the individual data source. Table 4 represents the proposed (observed) descriptive statistics for the pediatric population.

Table 4. Example Table of Descriptive Statistics

	All Doses*				
Patient Characteristic	# of COVID-19	Observed (Outcomes – [Outcome]		
	Vaccinations	#	Rate (per 100k person-years)		
Total	No data	No data	No data		
Sex	No data	No data	No data		
Female					
Male					
Age (years)	No data	No data	No data		
5-11					
12-15					
16-17					
Urban/Rural	No data	No data	No data		
Urban					
Rural					

³ For BNT162b2, the age groups will be: 6 months-4 years, 5-11 years, 12-15 years, and 16-17 years For mRNA-1273, the age groups will be: 6 months-5 years, 6-11 years, 12-15 years, and 16-17 years. For NVX-CoV2373, the age groups will be: 12-15 years and 16-17 years. For the "all brand" descriptive statistics, the age stratifications for BNT162b2 will be used where applicable.

	All Doses*			
Patient Characteristic	# of COVID-19	Observed Outcomes – [Outcome]		
	Vaccinations	#	Rate (per 100k person-years)	
HHS Region	No data	No data	No data	
[Region 1]				
[Region 2]				
[Region 3]				
[Region 4]				
[Region 5]				
[Region 6]				
[Region 7]				
[Region 8]				
[Region 9]				
[Region 10]				
Facility/Provider Type	No data	No data	No data	
Hospital				
Office				
Pharmacy				
Skilled Nursing Facility				
Home Health Agency				
Mass Immunization Center				
Others				

^{*} Additional statistics will be provided by individual doses

Note: Separate tables will be provided for each Data Partner.

4.6 Sequential Analyses for Safety Monitoring

For safety monitoring in the pediatric population, we will use the Poisson Maximized Sequential Probability Ratio Test (PMaxSPRT) to conduct sequential hypothesis tests for AESI labeled as RCA in Table 3.

The sequential analysis will test for an increased risk for each pediatric AESI following BNT162b2, mRNA-1273, or NVX-CoV2373 vaccination relative to expected rates. The PMaxSPRT sequential testing methodology will remain the same as in the Adult RCA where hypothesis tests will be continuously conducted until either a statistical signal occurs or until a maximum length of surveillance is reached which is defined in terms of observed events.

Proposed hypotheses, historical comparators, and testing specifications for this study will be discussed in subsequent sections.

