4.2 Study Period

The study start date will be the earliest EUA date for vaccination for each age group:

- BNT162b2
 - o Age 6 months-4 years: June 17th, 2022
 - o Age 5-11 years: October 29th, 2021
 - o Age 12-15 years: May 10th, 2021
 - Age 16-17 years: December 11th, 2020
- mRNA-1273:
 - o Age 6 months-17 years: June 17th, 2022
- NVX-CoV2373:
 - o Age 12-17 years: August 19th, 2022

Surveillance will continue through a pre-specified surveillance length, set for each AESI and age group to the number of events expected to be observed in the 6-month period from initiation of surveillance based on the incidence of the event estimated from historical data as well as the anticipated number of vaccine doses administered in the study population in this time period. The study period may be adjusted if additional vaccines for the pediatric population are approved.

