4.6.1 PMaxSPRT Specifications

Sequential analyses using the PMaxSPRT for pediatric-only outcomes will be conducted separately for each AESI (as listed in Table 3), data partner, and age group. Stratification adjustment by sex will be conducted where background rates permit. Similar to the adult RCA, for the purpose of the sequential

analysis, we will test for an increased risk of each AESI after primary series as the primary analysis, ⁴ and an increased risk for each AESI following each dose (dose 1, dose 2, and boosters/third doses separately) as the secondary analysis will be considered. If additional COVID-19 vaccines are approved in the future for the pediatric population in U.S., the analysis will also be stratified by vaccine brand. Other key parameters are described as follows:

Age Group Stratification: Analyses will be stratified by age groups (i.e., separate analyses will be performed for each age group):⁵

- BNT162b2: 6 months-4 years, 5-11 years, 12-15 years, and 16-17 years
- mRNA-1273: 6 months-5 years, 6-11 years, 12-15 years, 16-17 years
- NVX-CoV2373: 12-15 years and 16-17 years

Testing Frequency: Testing using the PMaxSPRT will occur on a monthly basis for OptumServe, CVS Health, and HCI. For individual AESI, at least three events must be observed to initiate sequential testing.

Statistical Hypotheses: We will conduct one-sided tests where the null hypothesis is that the observed rate of AESI in the vaccinated cohort is no greater than that in the historical comparator beyond a prespecified test margin, m ($m \ge 0$; expressed as a fraction of the comparator rate), and the alternative hypothesis is that the observed rate in the vaccinated cohort is greater than that in the comparator beyond the margin:

$$H_0: RR \le (1+m)$$

$$H_a: RR > (1+m)$$

Where 'RR' refers to the rate ratio comparing the post-vaccination rate with the expected rate. The test margin will be selected for each outcome similar to the adult RCA, based on expert guidance to ensure that large increases of risk will be detected while avoiding minimal increases that are unlikely to be clinically relevant. The specifications for test margins for all AESI for sequential testing are specified in Table 5.

14

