⁴ For BNT162b2 in ages 5-17 years and mRNA-1273 all ages, the primary series is defined as doses 1 and 2. For BNT162b2 in ages 6 months to 4 years, the primary series is defined as doses 1, 2 and 3. For NVX-CoV2373, the primary series is defined as doses 1 and 2 in ages 12-17 years.

⁵ Age groups selected to match ages included in EUA authorizations.

Table 5. List of AESI and Corresponding Test Margins for RCA Analysis

AESI for Sequential Testing	Test Margin (ages 6 months-4 years, BNT162b2, 6 months- 5 years, mRNA-1273)	Test Margin (ages 5 years-17 years, BNT162b2, 6 years-17 years, mRNA-1273, NVX- CoV2373)
Anaphylaxis	1.50	1.50
Appendicitis	1.09	1.25
Bell's Palsy	1.12	1.25
Common Site Thromboses with Thrombocytopenia	1.25	1.25
Deep Vein Thrombosis	1.25	1.25
Disseminated Intravascular Coagulation	1.25	1.25
Encephalomyelitis	1.73	2.50
Guillain Barre Syndrome	2.38	2.50
Hemorrhagic Stroke	1.25	1.25
Immune Thrombocytopenia	1.10	1.25
Myocarditis/Pericarditis (All Settings)*	1.50	1.50
Myocarditis/Pericarditis (IP,OP/ED)*	1.50	1.50
Narcolepsy	N/A	2.50
Non-Hemorrhagic Stroke	1.25	1.25
Pulmonary Embolism	1.25	1.25
Seizures/Convulsions	1.00	1.50

^{*} This includes all 4 myocarditis/pericarditis outcomes as specified in Table 3. If additional outcomes are added, test margins will be updated accordingly.

Significance Level and Number of Events to Signal: The significance level (alpha) of each sequential analysis will be set to 0.01. A stringent alpha level was specified to reduce the possibility of a large number of signals due to testing of multiple outcomes in a manner similar to previous applications of the PMaxSPRT. [42]

Length of Surveillance: The upper limit of surveillance is set for each AESI to the number of events expected to be observed in the 6-month period from initiation of surveillance, based on the incidence of the event estimated from historical data as well as the anticipated number of vaccine doses administered in the study population in this time period [44-45]. When estimating the anticipated number of vaccine doses in the study population in this time period, the following considerations were used:

- For BNT162b2 primary series in ages 5-17 years, we used historical influenza vaccination rates to estimate total vaccine uptake. As BNT162b2 was authorized first for ages 5-17 years, we assumed 100% of market share being assigned to BNT162b2 at surveillance initiation.

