 - For mRNA-1273 ages 6-11 years, 12-15 years, and 16-17 years and NVX-CoV2373 ages 12-15 years and 16-17 years, we will use the same vaccine uptake as was originally used for BNT162b2 ages 5-11 years, 12-15 years, and 16-17 years to ensure comparability of results.
- For BNT162b2 RCA of third/booster dose in age groups 5-11 years, 12-15 years and 16-17 years, we set the surveillance length to the expected number of events within a 6-month period assuming 30% uptake of the booster dose among the subset of persons eligible based on timing of completion of the primary series [46].

For BNT162b2 in ages 6 months-4 years and mRNA-1273 RCA in ages 6 months-5 years, we will
use the COVID-19 primary series vaccine uptake rate in the 5-11 year age group in the 6 months
following EUA to determine estimated total uptake. We assign each brand 100% of total
estimated uptake.

Critical Bound: Similar to the Adult RCA, the critical bound used for testing is calculated for each AESI and data partner. The critical bound is comprised of the series of critical values that are calculated for each testing point; an observed AESI rate that exceeds the critical value for a given test is defined as a signal. Calculation of the critical values is based on several pre-specified parameters: the upper limit of expected events (the maximum length of surveillance), the total alpha for the sequential analysis, the alpha spending plan, and the minimum number of events needed to signal. The critical bound is calculated using numerical procedures implemented in the R package 'Sequential' [47]

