4.6.2 Comparator Group Selection for PMaxSPRT

Similar to the FDA Adult RCA, the selection of the comparator group is influenced by several factors reflecting potential sources of confounding bias. One possible comparator group is the general population in each database. A separate background rates protocol has been developed to estimate background rates of AESI and evaluate possible comparator groups.

In brief, a pre-COVID-19 (i.e., historical) comparator population is defined for study period January 1, 2019 through December 31, 2019. A separate peri-COVID-19 population is defined using 2020 data. Within each population, AESI rates per person-time will be calculated for all enrollees in a given time period.

The following guidelines are used to select the comparator population by comparing pre-COVID-19 and peri-COVID-19 rates:

- If 95% confidence intervals of pre-COVID-19 and peri-COVID-19 periods overlap, pre-COVID-19 background rates will be selected as the comparator population
- If the 95% confidence intervals do not overlap because of low outcome counts (<50 counts) or seasonal fluctuations, pre-COVID-19 background rates will be selected as the comparator population
- If the 95% confidence intervals do not overlap because of large fluctuations, more stable background rates will be selected
- Otherwise, if none of the above conditions are satisfied, the time period with lower rate will be selected

Regardless of the ultimate comparator selected, calculated rates are stratified by age group and by sex if there are sufficient cases (5 or greater) in subgroups of the comparator population. The calculation of PMaxSPRT inputs will remain the same as the adult RCA wherein each test will compare an observed number of events to an expected number of events. The cumulative expected number of events will be based on the observed exposed person-time following any eligible dose occurring in each database and contain adjustments for observation delay due to partially accrued data and the implementation of the test margin in the statistical hypothesis.

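### Section 4.6 stops surveillance on observed events, but the critical bound is built for a cap in expected events; the cap's margin scale is also not stated

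*Protocol*

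**What the plan says.** The maximum length of surveillance is described in four places.

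- Section 4.6, in its account of the method carried over from the adult analysis: testing goes on until a signal or "until a maximum length of surveillance is reached which is defined in terms of observed events".
- Section 4.2: the length is "set for each AESI and age group to the number of events expected to be observed in the 6-month period from initiation of surveillance".
- Section 4.6.1, in the paragraph on surveillance length: "The upper limit of surveillance is set for each AESI to the number of events expected to be observed in the 6-month period". That number is said to be "based on the incidence of the event estimated from historical data as well as the anticipated number of vaccine doses administered".
- Section 4.6.1, Critical Bound: among the inputs to the critical values is "the upper limit of expected events (the maximum length of surveillance").

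Section 4.6.2 adds that the cumulative expected counts "contain adjustments for observation delay due to partially accrued data and the implementation of the test margin in the statistical hypothesis". Section 4.6.1 also fixes one-sided tests, monthly testing, a minimum of three events, and the error rate: "The significance level (alpha) of each sequential analysis will be set to 0.01".

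**The concern.** The same quantity is placed on two scales. A Poisson MaxSPRT bound computed for T expected events spends its alpha on the assumption that testing can continue until the cumulative expected count reaches T. A stop at T observed events ends sooner the higher the true rate is, so the rule would close testing earliest when there is a raised risk to find. Part of the alpha would go unspent.

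Analyses are split by AESI, data partner and age group, and also by vaccine and dose. That pushes T down, towards the range where the loss is largest. A stop at the cap without a signal could then be taken as more reassuring than it is.

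A second, smaller question concerns the margin. The running expected count includes it, while the description of the cap names only historical incidence and anticipated doses.

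**Working it through.** **The plan's own figures.** The only worked sequential figures are in Table 6 (m = 0). With E = n / risk ratio and LLR = n ln(n/E) − (n − E), the five rows give 0.331, 1.338, 3.871, 3.228 and 4.313, against the printed 0.33, 1.34, 3.87, 3.24 and 4.31. Month 4 is within the rounding of its risk ratio (3.211 to 3.246). The statistic is therefore the standard one. The printed bounds (2.27, 2.94) cannot be checked, because their upper limit and alpha spending are not given.

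Table 6 also shows the conflict. Suppose, for illustration only, a cap of 5, and take the printed bounds as given. Five events have been observed by month 2, with E = 5/2.30 = 2.17 and LLR 1.34, below 2.27. An observed-event cap stops there without a signal. An expected-event cap continues to month 3 (E = 11/2.65 = 4.15, still below 5), where LLR 3.87 exceeds 2.94 and the signal is found.

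**How early the observed cap stops.** Let k be the true rate divided by the null expected rate. T observed events accrue, on average, when the expected count is T/k, which is 1/k of the planned exposure. The LLR at that point is about T(ln k − 1 + 1/k):

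- T=5, k=3: 5 × (1.099 − 1 + 0.333) = 2.16
- T=10, k=2: 10 × (0.693 − 1 + 0.5) = 1.93
- T=10, k=3: 4.32
- T=20, k=2: 3.86
- T=50, k=2: 9.66

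The flat critical value needed below is about 3.8 to 3.9. The first two cases typically stop well short of it, T=20 sits on it, and T=50 is far beyond it.

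**Power.** From the plan: one-sided alpha 0.01, monthly looks, minimum 3 events. Assumed: six equal monthly increments of expected events, a flat bound, and T itself. The calculation is an exact Poisson recursion. The look at which the observed cap is crossed is still tested, which favours the plan.

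| T | k | Stop at T expected | Stop at T observed |
|---|---|---|---|
| 5 | 3 | 79% | 33% |
| 10 | 2 | 58% | 27% |
| 10 | 3 | 98% | 78% |
| 20 | 2 | 87% | 70% |
| 50 | 2 | 99.9% | 99.2% |

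Type I error at the null boundary is about 0.009 with the matched cap (discrete counts keep it just under 0.01). With the observed cap it is about 0.004 (T=5) to 0.008 (T=50).

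**The margin.** Write T0 for historical rate × anticipated exposure. The running expected count grows as (1+m) × T0 over that same exposure. If the cap is T0 unscaled, it is reached at a share 1/(1+m) of the exposure used to size it, whatever the true risk. With m read as section 4.6.1 defines it and Table 5 values of 1.00 to 2.50, that share is 1/2.00 = 50% down to 1/3.50 = 29%. If Table 5 lists null rate ratios instead, it is 1/1.00 = 100% down to 1/2.50 = 40%.

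For m = 1.25 and a true rate ratio of 4.5 (twice the null boundary of 2.25), power with a scaled and an unscaled expected cap is:

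- T0=5: 63% and 29.5%
- T0=10: 92% and 58%
- T0=20: 99.8% and 87%
- T0=50: above 99% for both

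Here the bound is computed for T0 and testing stops at T0, so the two match and alpha is kept.

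**The case against.** Section 4.6 is introductory and leaves the testing specifications to later sections. Its wording may be a loose shortening of events expected to be observed, and the operative text in 4.2 and 4.6.1 is on the expected scale. That is the likeliest intention, and if it is what is run, the power loss in the table does not occur. It does not remove the contradiction. Section 4.6 presents its rule as the adult method carried over unchanged, so the master protocol, which is not at hand, cannot be presumed to correct it.

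Three stronger readings are tempting and are not supported.

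- *The loss is as large as event-by-event testing suggests.* Under that scheme power falls from 76% to 15% (T=5, k=3), from 97% to 51% (T=10, k=3) and from 49% to 14% (T=10, k=2). Section 4.6 does speak of continuous testing, but section 4.6.1 fixes monthly tests, where the loss is smaller.
- *The cap omits the margin.* The text names no margin in the cap but does not exclude one, and section 4.6.2 refers the test inputs back to the adult analysis. This is an unstated scale, not a demonstrated error.
- *An unscaled cap breaks the error rate or the promised six months.* It does neither. It matches its own bound, and the 6-month period sizes an event count without promising a calendar duration. Its cost is exposure and power at any true risk, not especially when risk is raised.

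Monthly descriptive monitoring continues, and the work is signal detection, not evaluation. That tempers the consequence without repairing the rule.

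**Conclusion.** The stopping rule in section 4.6 is wrong as written: it contradicts sections 4.2 and 4.6.1 and does not match the bound computed for it. If it is followed, the loss of power is large for small T (46 percentage points at T=5, k=3; 31 at T=10, k=2; 20 at T=10, k=3), moderate at T=20 (17 points at k=2) and slight at T=50 (under 1 point at k=2). The error moves in the conservative direction, with type I error about 0.004 to 0.008. These sizes rest on assumed T, even accrual over six monthly looks and a flat bound; the protocol gives no T.

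The margin scale of the cap is a separate matter needing clarification. If the cap is unscaled, power falls but alpha and the match with the bound stand. If the cap already in use is in expected events with the margin included, only the text needs correcting.

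**What to change.** - **Section 4.6:** define the maximum length of surveillance by expected events under the null hypothesis, in place of observed events.
- **Sections 4.2 and 4.6.1 (Length of Surveillance):** state that the cap is on the same margin-adjusted scale as the cumulative expected count, that is (1+m) × historical rate × anticipated risk-window person-time for the analysis in question.

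The cost is a few sentences. Critical bounds need recomputing only if the unscaled cap was used. Any analysis already closed on an observed-event count should be identified, since its stop did not match its bound.

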4.6.1 PMaxSPRT Specifications

Sequential analyses using the PMaxSPRT for pediatric-only outcomes will be conducted separately for each AESI (as listed in Table 3), data partner, and age group. Stratification adjustment by sex will be conducted where background rates permit. Similar to the adult RCA, for the purpose of the sequential

analysis, we will test for an increased risk of each AESI after primary series as the primary analysis, ⁴ and an increased risk for each AESI following each dose (dose 1, dose 2, and boosters/third doses separately) as the secondary analysis will be considered. If additional COVID-19 vaccines are approved in the future for the pediatric population in U.S., the analysis will also be stratified by vaccine brand. Other key parameters are described as follows:

Age Group Stratification: Analyses will be stratified by age groups (i.e., separate analyses will be performed for each age group):⁵

- BNT162b2: 6 months-4 years, 5-11 years, 12-15 years, and 16-17 years
- mRNA-1273: 6 months-5 years, 6-11 years, 12-15 years, 16-17 years
- NVX-CoV2373: 12-15 years and 16-17 years

Testing Frequency: Testing using the PMaxSPRT will occur on a monthly basis for OptumServe, CVS Health, and HCI. For individual AESI, at least three events must be observed to initiate sequential testing.

Statistical Hypotheses: We will conduct one-sided tests where the null hypothesis is that the observed rate of AESI in the vaccinated cohort is no greater than that in the historical comparator beyond a prespecified test margin, m ($m \ge 0$; expressed as a fraction of the comparator rate), and the alternative hypothesis is that the observed rate in the vaccinated cohort is greater than that in the comparator beyond the margin:

$$H_0: RR \le (1+m)$$

$$H_a: RR > (1+m)$$

Where 'RR' refers to the rate ratio comparing the post-vaccination rate with the expected rate. The test margin will be selected for each outcome similar to the adult RCA, based on expert guidance to ensure that large increases of risk will be detected while avoiding minimal increases that are unlikely to be clinically relevant. The specifications for test margins for all AESI for sequential testing are specified in Table 5.

14

⁴ For BNT162b2 in ages 5-17 years and mRNA-1273 all ages, the primary series is defined as doses 1 and 2. For BNT162b2 in ages 6 months to 4 years, the primary series is defined as doses 1, 2 and 3. For NVX-CoV2373, the primary series is defined as doses 1 and 2 in ages 12-17 years.

⁵ Age groups selected to match ages included in EUA authorizations.

Table 5. List of AESI and Corresponding Test Margins for RCA Analysis

AESI for Sequential Testing	Test Margin (ages 6 months-4 years, BNT162b2, 6 months- 5 years, mRNA-1273)	Test Margin (ages 5 years-17 years, BNT162b2, 6 years-17 years, mRNA-1273, NVX- CoV2373)
Anaphylaxis	1.50	1.50
Appendicitis	1.09	1.25
Bell's Palsy	1.12	1.25
Common Site Thromboses with Thrombocytopenia	1.25	1.25
Deep Vein Thrombosis	1.25	1.25
Disseminated Intravascular Coagulation	1.25	1.25
Encephalomyelitis	1.73	2.50
Guillain Barre Syndrome	2.38	2.50
Hemorrhagic Stroke	1.25	1.25
Immune Thrombocytopenia	1.10	1.25
Myocarditis/Pericarditis (All Settings)*	1.50	1.50
Myocarditis/Pericarditis (IP,OP/ED)*	1.50	1.50
Narcolepsy	N/A	2.50
Non-Hemorrhagic Stroke	1.25	1.25
Pulmonary Embolism	1.25	1.25
Seizures/Convulsions	1.00	1.50

^{*} This includes all 4 myocarditis/pericarditis outcomes as specified in Table 3. If additional outcomes are added, test margins will be updated accordingly.

Significance Level and Number of Events to Signal: The significance level (alpha) of each sequential analysis will be set to 0.01. A stringent alpha level was specified to reduce the possibility of a large number of signals due to testing of multiple outcomes in a manner similar to previous applications of the PMaxSPRT. [42]

Length of Surveillance: The upper limit of surveillance is set for each AESI to the number of events expected to be observed in the 6-month period from initiation of surveillance, based on the incidence of the event estimated from historical data as well as the anticipated number of vaccine doses administered in the study population in this time period [44-45]. When estimating the anticipated number of vaccine doses in the study population in this time period, the following considerations were used:

- For BNT162b2 primary series in ages 5-17 years, we used historical influenza vaccination rates to estimate total vaccine uptake. As BNT162b2 was authorized first for ages 5-17 years, we assumed 100% of market share being assigned to BNT162b2 at surveillance initiation.
 - For mRNA-1273 ages 6-11 years, 12-15 years, and 16-17 years and NVX-CoV2373 ages 12-15 years and 16-17 years, we will use the same vaccine uptake as was originally used for BNT162b2 ages 5-11 years, 12-15 years, and 16-17 years to ensure comparability of results.
- For BNT162b2 RCA of third/booster dose in age groups 5-11 years, 12-15 years and 16-17 years, we set the surveillance length to the expected number of events within a 6-month period assuming 30% uptake of the booster dose among the subset of persons eligible based on timing of completion of the primary series [46].

For BNT162b2 in ages 6 months-4 years and mRNA-1273 RCA in ages 6 months-5 years, we will
use the COVID-19 primary series vaccine uptake rate in the 5-11 year age group in the 6 months
following EUA to determine estimated total uptake. We assign each brand 100% of total
estimated uptake.

Critical Bound: Similar to the Adult RCA, the critical bound used for testing is calculated for each AESI and data partner. The critical bound is comprised of the series of critical values that are calculated for each testing point; an observed AESI rate that exceeds the critical value for a given test is defined as a signal. Calculation of the critical values is based on several pre-specified parameters: the upper limit of expected events (the maximum length of surveillance), the total alpha for the sequential analysis, the alpha spending plan, and the minimum number of events needed to signal. The critical bound is calculated using numerical procedures implemented in the R package 'Sequential' [47]

